Appendix 5. Pandemic Risk Assessment and Mitigation Plan

In the event of an ongoing pandemic (such as COVID-19), potential risks associated with participants being unable to attend study visits have been identified for this study.

These risks can be summarized as follows:

- Study drug supplies to participants and sites:
 - Oral GS-6207 (600 mg and 300 mg doses) and SC GS-6207 study drug administration must occur at the study site. Dispensation of other oral study drug(s) must occur at the study site. Participants may be unable to return to the site for a number of visits to get the study drug, or the site may be unable to accept any participant visits. Without study drugs, the participant would not be able to stay on the study drug as planned per protocol.

Mitigation plan: Oral study drug supplies may be provided to the participant from the site without a clinic visit, once it is confirmed that the participant may safely continue on study drug as determined by the principal investigator (PI). A virtual visit must be performed prior to remote study drug resupply. At the earliest opportunity, the site will schedule in-person participant visits and return to the protocol's regular schedule of assessments. A qualified courier may be utilized to ship the study drug from sites to study participants if permitted by local ethic committee (EC)/institutional review boards (IRBs)/Regulatory Authority as applicable and with sponsor's approval. If a participant is attending a visit in-clinic and there is a risk that the next visit may not occur in-clinic, the site may dispense an additional bottle(s) of oral study drug(s) to the participant in anticipation of the missed visit. In such cases, a virtual visit will be performed if the participant is not able to come for in-person visit at the clinic. At the earliest opportunity, the site will schedule in-person participant visits and return to the protocol's regular schedule of assessments.

- Study drug shortage at site level.

Mitigation plan: The sites' study drug inventory should be closely monitored. Site staff should notify the sponsor or delegate if they foresee shortage in study drug inventory or if there is any interruption in local shipping service. The sponsor will continue to monitor inventory at the study drug depot and study sites. Manual shipments will be triggered as necessary.

- Participant safety monitoring and follow-up:
 - Participants cannot come to the study site for their scheduled study visits as required per protocol.

Mitigation plan: For participants who cannot come to the study site for their scheduled study visits as required per protocol, the PI or qualified delegate will conduct a virtual study visit, via phone or video conferencing, to assess the participant within target visit window date whenever possible. During the virtual study visit, the following information at minimum will be reviewed:

- Confirm if participant has experienced any adverse events (AEs)/serious adverse events (SAEs) and follow-up on any unresolved AE/SAEs.
- Review current list of concomitant medications and document any new concomitant medications.
- Review any changes in medical history.
- Confirm participant's oral study drug supply is sufficient to last until the next planned visit date. If study drug resupply is needed it will be provided as described above. GS-6207 SC dose can only be given at site. If participant is not able to come for in-person visit to receive GS-6207 SC dose at their scheduled visit, Sponsor should be notified receive guidance on next steps.
- Remind participant to maintain current oral dosing and to keep all dispensed study drug kits for return at the next on-site visit.

— Safety blood draws & central laboratory analysis cannot be done.

Mitigation plan: Local labs may be utilized as appropriate to monitor participant safety until the participant can return to the site for their regular follow-up per protocol per PI discretion. Any laboratory assessments conducted at a local lab due to the pandemic will be documented accordingly.

— Participants are unable to attend the study visit to sign an updated informed consent form (ICF) version.

Mitigation plan: The site staff will follow their approved consent process and remain in compliance with local EC/IRB and national laws and regulations. Remote consent will be allowed if approved by the local EC/IRB. The consent process will be documented and confirmed by normal consent procedure at the earliest opportunity.

- Protocol and monitoring compliance:

— Protocol deviations in case scheduled visits cannot occur as planned per protocol.

Mitigation plan: If it is not possible to complete a required procedure at scheduled visit, the visit should be conducted as soon as possible when conditions allow. The situation should be recorded and explained as a protocol deviation (PD). Any missed participant visits or deviation to the protocol due to the pandemic must be reported in the e-case report form (CRF) and described in the clinical study report. Any virtual study visits that are conducted in lieu of clinic visits due to the pandemic will be documented as a PD related to the pandemic.

— On-site monitoring visit is not feasible.

Monitors may be unable to carry out source data review (SDR) or source data verification (SDV), study drug accountability, or protocol and GCP compliance. This may lead to delays in SDV, an increase in protocol deviations, or under reporting of AEs.

Mitigation plan: The study monitor is to remain in close communication with the site to ensure data entry and query resolution (remote SDV not allowed). The study monitor is to reference the Study Monitoring Plan for guidance on how to conduct a remote monitoring visit. The study staff is to save and document all relevant communication in the study files. The status of sites that cannot accept monitoring visits and/or participants on site, must be tracked centrally and updated on a regular basis.

- Missing data and data integrity:

— Increased number of missing data due to participants missing visits/assessments. This could have an impact on the analysis and the interpretation of clinical trial data.

Mitigation plan: Implications of a pandemic on methodological aspects for the study will be thoroughly assessed and documented, and relevant actions will be taken as appropriate (ie, modification of the statistical analysis plan) and in compliance with Regulatory Authorities' guidance. Overall, the clinical study report will describe the impact of the pandemic on the interpretability of study data.

Virtual visits should be documented in the participant's source documents. For any completed virtual visits, associated data will be entered in EDC and a general comment will be added noting that the visit was completed virtually due to pandemic.

Risks will be assessed continuously, and temporary measures will be implemented to mitigate these risks as part of a mitigation plan, as described above. These measures will be communicated to the relevant stakeholders as appropriate and are intended to provide alternate methods that will ensure the evaluation and assessment of the safety of participants who are enrolled in this study.

Since these potential risks would be considered mitigated with the implementation of these measures, the expected benefit risk assessment of study drug(s) in study participants remains unchanged.

T_{max}	time (observed time point) of C_{max}
λ_z	terminal elimination rate constant, estimated by linear regression of the terminal elimination phase of the concentration of drug versus time curve

1. INTRODUCTION

This statistical analysis plan (SAP) describes the statistical analysis methods and data presentations to be used in tables, figures, and listings (TFLs) of Week 54 interim analysis for Study GS-US-200-4334, the primary analysis of this study. A formal interim analysis will be performed when all subjects have completed Week 54 assessment or prematurely discontinued from study drug. The purpose of this interim analysis is to support the lenacapavir (LEN; GS-6207) regulatory filing for the indication in the heavily treatment experienced people with HIV (PWH).

This SAP is based on the study protocol amendment 3 dated 01 September 2020 and the electronic case report form (eCRF). The SAP will be finalized prior to data finalization for the Week 54 analysis. Any changes made after the finalization of the SAP will be documented in the clinical study report (CSR).

1.1. Study Objectives

The primary objective of this study is as follows:

- To evaluate the efficacy of LEN containing regimens in PWH as determined by the proportion of subjects with HIV-1 RNA < 50 copies/mL at Week 54

The secondary objectives of this study are as follows:

- To evaluate the efficacy of LEN containing regimens in PWH as determined by the proportion of subjects with HIV-1 RNA < 50 copies/mL at Weeks 28, 38, and 80
- To evaluate the change from baseline in log₁₀ HIV-1 RNA and in CD4+ cell count at Weeks 28, 38, 54, and 80
- To evaluate the safety and tolerability of the LEN containing regimens through 28, 38, 54, and 80 weeks of treatment
- To evaluate the pharmacokinetics (PK) of LEN, bictegravir (BIC), and tenofovir alafenamide (TAF)

1.2. Study Design

Design Configuration and Subject Population

This is a Phase 2, randomized, open label, active controlled, multicenter study.

Approximately 175 treatment-naive PWH who meet all eligibility criteria will be randomized in a 2:2:2:1 ratio to 1 of the following 4 treatment groups. Randomization will be stratified by HIV-1 RNA level ($\leq 100,000$ copies/mL or $> 100,000$ copies/mL) at screening.

Treatment Groups

Treatment Group 1 (n = 50)

Induction: Subjects will receive oral LEN 600 mg, 600 mg, and 300 mg, without regard to food, at Days 1, 2, and 8 respectively. Subjects will also begin oral daily emtricitabine (F)/TAF (200/25 mg), without regard to food from Day 1 onwards for a total of 28 weeks. On Day 15 subjects will receive subcutaneous (SC) LEN 927 mg, without regard to food.

Maintenance: Subjects will receive SC LEN 927 mg at Week 28 and every 26 weeks thereafter. Subjects will discontinue oral daily F/TAF (200/25 mg) at Week 28 and begin taking oral daily TAF (25 mg), without regard to food.

Treatment Group 2 (n = 50)

Induction: Subjects will receive oral LEN 600 mg, 600 mg, and 300 mg, without regard to food at Days 1, 2, and 8 respectively. Subjects will also begin oral daily F/TAF (200/25 mg), without regard to food from Day 1 onward for a total of 28 weeks. On Day 15 subjects will receive SC LEN 927 mg, without regard to food.

Maintenance: Subjects will receive SC LEN 927 mg at Week 28 and every 26 weeks thereafter. Subjects will discontinue oral daily F/TAF (200/25 mg) at Week 28 and begin oral daily BIC (75 mg) without regard to food.

Treatment Group 3 (n = 50)

Subjects will receive oral LEN 600 mg and 600 mg without regard to food at Days 1 and 2, respectively. On Day 3, subjects will begin oral daily LEN 50 mg, without regards to food. Subjects will begin oral daily F/TAF (200/25 mg), without regard to food from Day 1 onwards.

Treatment Group 4 (n = 25)

Subjects will receive oral daily bictegravir/emtricitabine/TAF (B/F/TAF, 50/200/25 mg), without regard to food at Day 1 and throughout their participation in the study.

Key Eligibility Criteria

Treatment naive PWH who meet the following criteria:

- Age \geq 18 years of age at Screening
- Plasma HIV-1 RNA \geq 200 copies/mL at Screening
- CD4+ cell count \geq 200 cells/ μ L at Screening
- Antiretroviral (ARV) naive with no use of any ARV medications within one month of Screening. Use of pre-exposure prophylaxis (PrEP) (any duration), post-exposure prophylaxis (PEP) (any duration), or HIV-1 treatment ($<$ 10 days therapy total) $>$ 1 month prior to Screening is permitted.

Schedule of Assessments

At screening, laboratory analyses (hematology, chemistry, and urinalysis, and serum pregnancy test [for women]), HIV-1 RNA, CD4+ cell count, vital signs, electrocardiogram (ECG), complete physical examination and estimated glomerular filtration rate (eGFR) will be performed, and hepatitis B virus (HBV) and hepatitis C virus (HCV) serologies will be analyzed. Analysis of the subject's HIV-1 resistance to support eligibility will be completed.

After screening procedures, eligible subjects will be randomized into 1 of the 4 treatment groups in a 2:2:2:1 ratio.

Subjects in Treatment Groups 1, 2, and 3 only, will have visits on Day 1, Day 2, CCI [REDACTED] Day 8, and Day 15. All subjects will have a Week 4 visit and will continue to attend study visits every 6 weeks until Week 28.

Subjects in Treatment Groups 1 and 2 will need to have HIV-1 RNA results < 50 copies/mL at Weeks 16 and 22 to initiate treatment with a two agent regimen at Week 28; those with values \geq 50 copies/mL will discontinue the study drug at or prior to Week 28.

After Week 28, subjects will attend study visits on Week 38, Week 54, Week 64, and Week 80. After Week 80, subjects in Treatment Group 4 will complete the study and subjects in Treatment Groups 1, 2, and 3 will be given the option to receive further treatment and continue to attend visits alternating between every 10 weeks and every 16 weeks visits.

At each visit, adverse events (AEs), concomitant medications, laboratory tests, physical examinations, PK, and patient reported outcomes (PROs) will be performed in accordance with the Study Procedures Table.

More details for study procedures could be found in Section 12 ([Appendix 1](#)).

Study Duration

Duration of treatment is at least 80 weeks. Subjects in Treatment Group 4 will complete the study at Week 80.

Following successful completion of Week 80 visit, subjects receiving LEN will be given the option to receive further treatment and continue to attend visits on Week 90, Week 106, Week 116, Week 132, Week 142, and will continue to alternate between every 10 weeks and every 16 weeks visits. Subjects willing to continue the study beyond Week 80 in Treatment Groups 1 and 2 will continue to receive SC LEN 927 mg every 6 months (26 weeks) from Week 80 onwards and subjects in Treatment Group 3 will receive oral LEN 50 mg daily from Week 80 until the product becomes accessible to subjects through an access program, or until Gilead elects to discontinue the study in the country. Subjects in Treatment Groups 1, 2, and 3 will also receive TAF, F/TAF, or BIC as applicable.

Subjects who discontinue study drugs prior to Week 80 visit or prior to study completion may be required to complete 30-Day, 90-Day and/or 180-Day Follow Up visits after Early Termination Visit.

1.3. Sample Size and Power

A sample size of 50 subjects in Treatment Groups 1 to 3, respectively, was chosen to estimate the response rate of HIV-1 RNA < 50 copies/mL at Week 54. A total sample size of 75 subjects for each pair of comparisons (ie, between each of the LEN-containing regimen groups [Treatment Groups 1 to 3, n = 50] and the B/F/TAF [Treatment group 4, n = 25]) will provide 39% power to evaluate non-inferiority with respect to the response rate of HIV-1 RNA < 50 copies/mL at Week 54. In this sample size and power calculation, it is assumed a response rate is 90.9% (based on pooled data from Studies GS-US-380-1489 and GS-US-380-1490) for each treatment group and a non-inferiority margin is 0.12.

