Baseline disease characteristics were similar across the treatment groups. Overall, the median (Q1, Q3) baseline HIV-1 RNA value was 4.37 (3.86, 4.74) \log_{10} copies/mL, and the median (Q1, Q3) baseline CD4 cell count was 437 (332, 599) cells/ μ L. Among the 182 participants, most had HIV-1 RNA \leq 100,000 copies/mL (85.2%, 155 participants) and a CD4 cell count range of \geq 350 to $<$ 500 cells/ μ L (31.9%, 58 participants) or \geq 500 cells/ μ L (37.4%, 68 participants).

Efficacy Results:

Primary Efficacy End Point

HIV-1 RNA $<$ 50 copies/mL at Week 54 Using the US FDA-Defined Snapshot Algorithm

The primary analysis at Week 54 demonstrated similar results in each treatment group, with no significant difference between each of the GS-6207-containing groups and the BVY group, as follows:

- GS-6207 total: 136 of 157 participants (86.6%)
- SC GS-6207 + (DVY \rightarrow TAF): 47 of 52 participants (90.4%)
- SC GS-6207 + (DVY \rightarrow BIC): 45 of 53 participants (84.9%)
- Oral GS-6207 + DVY: 44 of 52 participants (84.6%)
- BVY: 23 of 25 participants (92.0%)

For participants with HIV-1 RNA $<$ 50 copies/mL at Week 28, the proportion with HIV-1 RNA $<$ 50 copies/mL at Week 54 using the US FDA-defined snapshot algorithm were also similar in each treatment group, with no significant difference between each of the GS-6207-containing groups and the BVY group, as follows:

- GS-6207 total: 135 of 147 participants (91.8%)
- SC GS-6207 + (DVY \rightarrow TAF): 46 of 49 participants (93.9%)
- SC GS-6207 + (DVY \rightarrow BIC): 45 of 49 participants (91.8%)
- Oral GS-6207 + DVY: 44 of 49 participants (89.8%)
- BVY: 23 of 25 participants (92.0%)

Secondary Efficacy End Points

Week 28

Results from the secondary efficacy analysis of Week 28 data of Study GS-US-200-4334 demonstrated similar results in each treatment group, with no significant difference between each of the GS-6207-containing treatment groups and the BVY treatment group with respect to the proportion of participants with HIV-1 RNA < 50 copies/mL using the US FDA-defined snapshot algorithm, the change from baseline in log₁₀ HIV-1 RNA, and the change from baseline in CD4 cell count.

HIV-1 RNA < 50 copies/mL using the US FDA-defined snapshot algorithm

- GS-6207 total: 147 of 157 participants (93.6%)
- SC GS-6207 + (DVY → TAF): 49 of 52 participants (94.2%)
- SC GS-6207 + (DVY → BIC): 49 of 53 participants (92.5%)
- Oral GS-6207 + DVY: 49 of 52 participants (94.2%)

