8.10. Sample Size

A sample size of 50 participants in Treatment Groups 1 to 3, respectively, was chosen to estimate the response rate of HIV-1 RNA < 50 copies/mL at Week 54. A total sample size of 75 participants for each pair of comparisons (ie, between each of the GS-6207-containing regimen groups [Treatment Groups 1 to 3, n = 50] and the B/F/TAF [Treatment group 4, n = 25]) will provide 39% power to evaluate non-inferiority with respect to the response rate of HIV-1 RNA < 50 copies/mL at Week 54. In this sample size and power calculation, it is assumed a response rate is 90.9% (based on pooled data from studies GS-US-380-1489 and GS-US-380-1490) for each treatment group and a non-inferiority margin is 0.12.

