2. TYPE OF PLANNED ANALYSIS

2.1. Interim Analyses

2.1.1. Data Monitoring Committee Analysis

One external multidisciplinary Data Monitoring Committee (DMC) analysis was conducted after all subjects have completed their Week 16 visit or prematurely discontinued from study drug, all outstanding data queries had been resolved or adjudicated as unresolvable, and the data had been cleaned and finalized for the analysis. No formal stopping rules was used by the DMC for safety outcomes. Rather, a clinical assessment was made to determine if the nature, frequency, and severity of AEs associated with a study treatment warrant the early termination of the study in the best interest of the subjects. No alpha penalty will be applied for the primary analysis of the primary efficacy endpoint given that the study is not adequately powered for a formal efficacy evaluation. The purpose of the interim analysis was to provide the DMC with a statistical report for review. More details are documented in the DMC charter.

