3. GENERAL CONSIDERATIONS FOR DATA ANALYSES

Analysis results will be presented using descriptive statistics. For categorical variables, the number and percentage of subjects in each category will be presented; for continuous variables, the number of subjects (n), mean, standard deviation (SD) or standard error (SE), median, first quartile (Q1), third quartile (Q3), minimum, and maximum will be presented.

All statistical tests will be 2-sided and performed at the 5% significance level for descriptive purpose unless otherwise specified.

By-subject listings will be presented for all subjects in the All Randomized Analysis Set and sorted by subject identification (ID) number, visit date, and time (if applicable). Data collected on log forms, such as AEs, will be presented in chronological order within the subject. The treatment group to which subjects were randomized will be used in the listings. Age, sex at birth, race, and ethnicity will be included in the listings, as space permits.

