6.1.2. Primary Analysis of the Primary Efficacy Endpoint

The proportion of subjects with HIV-1 RNA < 50 copies/mL as determined by the US FDA-defined snapshot algorithm at Week 54 will be based on the FAS. Point estimates ($P_1 - P_2$) and its 95% confidence interval (CI) for the difference in the response rates between each of the LEN-containing regimen groups (Treatment Groups 1 to 3) and the B/F/TAF group (Treatment Group 4) will be constructed using stratum-adjusted Mantel-Haenszel (MH) proportion as described as follows {Koch 1989}, stratified by baseline HIV-1 RNA level ($\leq 100,000$ copies/mL or $> 100,000$ copies/mL):

$$P_1 - P_2 \pm Z_{(1-\alpha/2)} * SE(P_1 - P_2),$$

where

- $(P_1 - P_2) = \frac{\sum w_h d_h}{\sum w_h}$, is the stratum-adjusted MH proportion difference,

where $d_h = p_{1h} - p_{2h}$ is the difference in the response rate between of the LEN-containing regimen groups (Treatment Groups 1 to 3) and the B/F/TAF group (Treatment Group 4) in stratum h ($h=1$ to 4).

- $w_h = \frac{n_{1h} n_{2h}}{n_{1h} + n_{2h}}$, is the weight based on the harmonic mean of sample size per treatment group for each stratum where n_{1h} and n_{2h} are the sample sizes of the LEN-containing regimen groups (Treatment Groups 1 to 3) and the B/F/TAF group (Treatment Group 4) in stratum h .

- $SE(P_1 - P_2) = \sqrt{\frac{\sum w_h^2 \left[\frac{p_{1h}^* (1 - p_{1h}^*)}{n_{1h} - 1} + \frac{p_{2h}^* (1 - p_{2h}^*)}{n_{2h} - 1} \right]}{(\sum w_h)^2}}$, where $p_{1h}^* = \frac{m_{1h} + 0.5}{n_{1h} + 1}$ and

$p_{2h}^* = \frac{m_{2h} + 0.5}{n_{2h} + 1}$. m_{1h} and m_{2h} are the number of subjects with HIV-1 RNA < 50 copies/mL in the LEN-containing regimen groups (Treatment Groups 1 to 3) and the B/F/TAF group (Treatment Group 4) in stratum h .

- $\alpha = 0.05$ for this study
- $Z_{(1-\alpha/2)} = Z_{0.9750} = 1.96$ is the 97.50th percentile of the normal distribution

Note that if the computed lower confidence bound is less than -1 , the lower bound is defined as -1 . If the computed upper confidence bound is greater than 1 , the upper bound is defined as 1 .

The number and percentage of subjects with HIV-1 RNA < 50 copies/mL at Week 54 will be summarized. The associated p-values will be estimated based on the CMH test stratified by baseline HIV-1 RNA level ($\leq 100,000$ copies/mL or $> 100,000$ copies/mL).

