10. SOFTWARE

SAS® Software Version 9.4. SAS Institute Inc., Cary, NC, USA.

nQuery Advisor(R) Version 7.0. Statistical Solutions, Cork, Ireland.

Phoenix WinNonlin® 7.0 Pharsigh Corporation, Princeton, NJ, USA.

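### The 39% power in SAP 1.3 belongs to a simple unadjusted interval; the interval planned in SAP 6.1.2 is wider (expected 95% half-width about 0.155 v 0.138) and gives about 26% at margin 0.12 if response is equal across strata

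*SAP*

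**What the plan says.** SAP 1.3 gives two purposes for the sample size. The 50 participants in each of Treatment Groups 1 to 3 "was chosen to estimate the response rate of HIV-1 RNA < 50 copies/mL at Week 54". Each comparison with the 25 participants on B/F/TAF "will provide 39% power to evaluate non-inferiority with respect to the response rate of HIV-1 RNA < 50 copies/mL at Week 54", assuming 90.9% response in every group and a margin of 0.12. Protocol 8.10 carries the same figure. Neither section names a formula or an alpha for the 39%. SAP 10 lists sample-size software ("nQuery Advisor(R) Version 7.0. Statistical Solutions, Cork, Ireland") but no method.

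SAP 6.1.2 defines the interval for the primary comparison. The difference and its 95% limits "will be constructed using stratum-adjusted Mantel-Haenszel (MH) proportion as described as follows", stratified by baseline HIV-1 RNA (at or below v above 100,000 copies/mL). The standard error replaces each observed rate by (m+0.5)/(n+1) and divides by n-1, separately in each treatment-by-stratum cell.

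On the status of inference, SAP 3 says: "All statistical tests will be 2-sided and performed at the 5% significance level for descriptive purpose unless otherwise specified". SAP 2.1.1 waives an alpha penalty "given that the study is not adequately powered for a formal efficacy evaluation".

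**The concern.** A reader takes a stated power to describe the analysis that will be run. Here the power matches a plain interval with ordinary variance, while the planned interval has a variance that is inflated on purpose, and inflated most in small cells. With 25 control participants split over two strata, some cells hold only a handful of people. If the inflation matters, SAP 1.3 gives a more favourable picture than its own primary interval delivers. It also gives no precision at all, although estimation is the first purpose it names.

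**Working it through.** **Inputs.** n = 50 v 25, response 90.9% in both groups and margin 0.12 (SAP 1.3); critical value 1.96, weights and standard error (SAP 6.1.2). Assumed: one-sided 0.025, which matches the lower limit of a 95% interval; two strata, since only two are named; equal response in both strata unless stated. No planned stratum share is given. Protocol 1.2.2.8 reports most participants at or below 100,000 "copies/mL (85.2%, 155 participants" of 182), so 27/182 = 14.8% were above, or roughly 7 of 50 and 4 of 25. I used 8-30% as a range around this.

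**Step 1: reproduce the 39%.**
- SE = sqrt(0.909 × 0.091 × (1/50 + 1/25)) = 0.0704.
- Half-width = 1.96 × 0.0704 = 0.138.
- Power = Φ(0.12/0.0704 − 1.96) = 39.9%.
- Exact binomial enumeration of the unstratified Wald interval gives 39.3%.
- One-sided 0.05 would give 52% and a continuity correction 25%; neither matches.

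**Step 2: the planned interval.** The estimate is Σw_h d_h / Σw_h with w_h = n1h·n2h/(n1h+n2h). The variance is Σw_h²[p1*(1−p1*)/(n1h−1) + p2*(1−p2*)/(n2h−1)] / (Σw_h)², with p* = (m+0.5)/(n+1). As an illustration, a cell of 4 in which all respond has p* = 4.5/5 = 0.9 and contributes 0.9 × 0.1/3 = 0.030. The ordinary estimate there is 0, and the true value at 90.9% is 0.909 × 0.091/4 = 0.021.

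Exact enumeration over all outcomes, margin 0.12:

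| Interval | Expected half-width | Chance lower limit > −0.12 |
|---|---|---|
| Planning formula | 0.138 | 39.9% |
| Unstratified Wald | 0.133 | 39.3% |
| Stratified MH, ordinary variance | 0.130 | 40.3-42.4% |
| SAP variance, no strata | 0.145 | 38.3% |
| SAP 6.1.2 as planned, two strata | 0.154-0.157 | 25.4-26.6% |

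The ranges cover splits from 46/4 v 23/2 to 35/15 v 17/8. For 43/7 v 21/4 the planned interval gives 26.3% and 0.154. Simulation with random stratum sizes gives 25.8-26.4% and 0.154-0.156. Coverage of the planned interval is 97.1-97.5%, so it is conservative.

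**Step 3: source of the loss.** Stratification with ordinary variance loses nothing. At margin 0.12 the adjustment without strata costs about one point (39.3% to 38.3%), so nearly all of the drop to 26% comes from applying it inside small stratum cells. Averaged over margins 0.10-0.15, the split is nearer half and half: 45.4% (Wald), 37.6% (adjusted, no strata), 30.5-31.9% (planned).

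**Step 4: sensitivity to the margin.** Outcomes are discrete, so the percentage moves in jumps. For 43/7 v 21/4 it is 26.3% at 0.12, 31.0% at 0.125 and 37.2% at 0.13. With equal response, the planned interval still lies 6.5-15.3 points below the planning formula at every margin from 0.10 to 0.15.

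**Step 5: unequal response by stratum**, overall rate held at 90.9%, 43/7 v 21/4, margin 0.12:

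| High v low stratum | Power |
|---|---|
| 80% v 93% | 29% |
| 70% v 94% | 32% |
| 60% v 96% | 37% |
| 50% v 98% | 43% |

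The documents give no response rates by stratum, so no upper bound can be put on the figure without stating them.

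**The case against.** The strongest reply is that the 39% is correct for its inputs, that neither document ties it to the SAP 6.1.2 interval, and that a simple planning formula followed by a stratified analysis is common practice. SAP 6.1.2 contains no non-inferiority rule, and the plan already calls itself underpowered and descriptive, so 39% and 26% carry the same message.

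Most of this stands. It settles the severity, and it rules out calling the 39% an arithmetic error. It does not make the figure true of the one interval that the SAP plans for these comparisons. If the results are descriptive, the width of that interval is what a reader most needs, and it is missing.

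Three stronger readings are tempting, and the documents do not support them.
- A reader might infer that Protocol 8.10 is also wrong, because it says that the design "will provide 39% power to evaluate non-inferiority with respect to the response rate". But Protocol 8.5.1 specifies only a normal approximation stratified by HIV-1 RNA. With ordinary variance that gives about 40-42%, so the protocol's figure is consistent with the protocol's own method.
- A reader might infer a still larger loss, because SAP 6.1.2 indexes strata from 1 to 4. SAP 3.3 and the text of 6.1.2 name only the two HIV-1 RNA levels, so a four-stratum figure would need an invented second factor.
- A reader might infer that the trial was sized wrongly or that its primary interval is unsound. The interval errs on the wide side, and nothing in the plan turns on crossing -0.12.

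**Conclusion.** The point holds and is minor. SAP 1.3 states a power that the interval in SAP 6.1.2 does not deliver under the SAP's own planning inputs. The expected half-width is about 0.155 rather than 0.138, and the chance of clearing -0.12 is about 26% rather than 39%. This rests on one-sided 0.025, two strata, 90.9% response in both groups and both strata, and 8-30% of participants in the high stratum. The half-width is the firmer of the two figures. The 26% applies to equal response across strata and should not be quoted without that condition: the planned interval reaches 39% only when response in the high stratum falls below about 60%. The attribution of the 39% to an unstratified formula is by reproduction, since the SAP does not name its method.

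**What to change.** Clarify SAP 1.3 only. SAP 1 provides that changes after finalization are documented in the clinical study report, so record it there. Keep the 39% as the planning figure and, once the sponsor's calculation record confirms it, state that it comes from an unstratified normal approximation at one-sided 0.025. Then add wording such as: For each comparison with B/F/TAF (50 v 25), the interval planned in Section 6.1.2 has an expected 95% half-width of about 0.155 and, at margin 0.12, about 26% power. This assumes one-sided 0.025, 90.9% response in both groups and both HIV-1 RNA strata, and 8-30% of participants above 100,000 copies/mL; the power would be higher if response differs by stratum.

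Leave Protocol 8.10 and the primary interval as they are. Do not add a -12% criterion: Protocol 1.2.2.8 already reports the Week 54 results, so any such rule would be set after the fact.

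The cost is a few sentences and a less favourable stated figure. No analysis, decision rule or number of participants changes.
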